	Author(s): [name], [name], [name]	Version: v2.1
	Dissemination level: Public	

Study Title	DARWIN EU® – Effectiveness of COVID-19 vaccines on severe COVID-19 and post-acute outcomes of SARS-CoV-2 infection
Protocol version identifier	V2.1
Date of last version of protocol	10/05/2024
EU PAS register number	EUPAS107615
Active substance	COVID-19 vaccines BNT162b2 and mRNA-1273
Medicinal products	
Comirnaty: Comirnaty original strain (monovalent), Comirnaty original strain + omicron ba1 (adapted, bivalent), Comirnaty original strain + omicron ba4/5 (adapted, bivalent)
 
Spikevax: Spikevax original strain (monovalent), Spikevax original strain + omicron ba1 (adapted, bivalent), Spikevax original strain + omicron ba4/5 (adapted, bivalent)

Research question and objectives	
Research question: What is the effectiveness of the EMA-authorized COVID-19 vaccines Comirnaty and Spikevax against severe COVID-19 and post-acute outcomes of SARS-CoV-2 infection?
 
The objectives of the study are:
 
 1. To assess the effectiveness of COVID-19 vaccination for the prevention of severe COVID-19 related outcomes (COVID-19 related hospitalization or COVID-19 related death) 2. To assess waning of the effectiveness of COVID-19 vaccination for the prevention of severe COVID-19 related outcomes (COVID-19 related hospitalization or COVID-19 related death) 3. To assess the effectiveness of COVID-19 vaccination for the prevention of all-cause mortality in the 3- and 6-months following discharge for COVID-19 related hospitalization 4. To assess the effectiveness of COVID-19 vaccination for the prevention of new-onset type 1 Diabetes Mellitus in the 12 months after a SARS-CoV-2 infection 5. To assess the effectiveness of COVID-19 vaccination for the prevention of new-onset type 2 Diabetes Mellitus in the 12 months after a SARS-CoV-2 infection 6. To assess the effectiveness of COVID-19 vaccination for the prevention of cardiovascular events in the 12 months after a SARS-CoV-2 infection
Countries of study	Spain, The UK, The Netherlands
Author	[name], [name] and [name]

	Phase II C3-002 – Study Protocol	
	Author(s): [name], [name], [name]	Version: v2.1
		Dissemination level: Public

LIST OF ABBREVIATIONS

Abbreviation	Name
CDM	Common Data Model
COVID-19	Coronavirus disease-2019
EHR	Electronic Health Record
ENCePP	European Network of Centres for Pharmacoepidemiology and Pharmacovigilance
ICU	Intensive care unit
OMOP	Observational Medical Outcomes Partnership
SARS-CoV-2	Severe acute respiratory syndrome coronavirus 2
RT-PCR	Reverse transcription polymerase chain reaction
IRR	Incidence rate ratio
CPRD	Clinical Practice Research Datalink
IPCI	Integrated Primary Care Information
SIDIAP	The Information System for Research in Primary Care
SNOMED	Systematized Nomenclature of Medicine

	Phase II C3-002 – Study Protocol	
	Author(s): [name], [name], [name]	Version: v2.1
		Dissemination level: Public

1. TITLE

DARWIN EU® – Effectiveness of COVID-19 vaccines on severe COVID-19 and post-acute outcomes of SARS-CoV-2 infection

3. ABSTRACT (STAND ALONE SUMMARY OF THE STUDY PROTOCOL)

Title

DARWIN EU® – Effectiveness of COVID-19 vaccines on severe COVID-19 and post-acute outcomes of SARS-CoV-2 infection

Rationale and Background

The research agenda of the Vaccine Monitoring Platform jointly coordinated by EMA and the European Centre for Disease Prevention and Control (ECDC) includes the continuous assessment of COVID-19 vaccine effectiveness.

COVID-19 vaccines were authorised for use in the European Union. These vaccines, and any (future) adapted vaccines, would therefore benefit from post-authorisation studies to provide real-world evidence to guide regulatory and vaccination policies. A recent post-authorisation study performed in the Nordic countries, where near real-time data is available, showed that receipt of a bivalent BA4/5 mRNA booster as a fourth dose provides 67.8% protection against COVID-19 related hospitalisation. There is also evidence that effectiveness starts to wane after a few months. For regulatory purposes, such data are especially useful for the most recent variants, including XBB and later.

There is mounting evidence on post-acute outcomes of SARS-CoV-2 infection. This can include very specific outcomes such as cardiovascular events or the incidence of new-onset diabetes, or broader definitions such as the WHO clinical case definition for post COVID-19 condition. Data are needed regarding the COVID-19 vaccines effectiveness at preventing these outcomes. This is pertinent for the most recent variants, but equally important for older variants.

Objective(s)

To generate additional evidence on the effectiveness of COVID-19 vaccines at preventing severe COVID-19 and post-acute outcomes of SARS-CoV-2 infection.

Specifically, this study has 6 objectives:

1. To assess the effectiveness of COVID-19 vaccination for the prevention of severe COVID-19 related outcomes (COVID-19 related hospitalisation or COVID-19 related death)
2. To assess waning of the effectiveness of COVID-19 vaccination for the prevention of severe COVID-19 related outcomes (COVID-19 related hospitalisation or COVID-19 related death)
3. To assess the effectiveness of COVID-19 vaccination for the prevention of all-cause mortality in the 3- and 6-months following discharge for COVID-19 related hospitalisation
4. To assess the effectiveness of COVID-19 vaccination for the prevention of new-onset type 1 Diabetes Mellitus in the 12 months after a SARS-CoV-2 infection
5. To assess the effectiveness of COVID-19 vaccination for the prevention of new-onset type 2 Diabetes Mellitus in the 12 months after a SARS-CoV-2 infection
6. To assess the effectiveness of COVID-19 vaccination for the prevention of cardiovascular events in the 12 months after a SARS-CoV-2 infection

	Phase II C3-002 – Study Protocol	
	Author(s): [name], [name], [name]	Version: v2.1
		Dissemination level: Public

Research Methods

Study design: Population-level cohort studies

Data sources:

- Clinical practice Research Datalink (CPRD) GOLD, United Kingdom
- Integrated Primary Care Information Project (IPCI), The Netherlands
- The Information System for Research in Primary Care (SIDIAP), Spain

Additional databases can be added as part of a routine repetition of this study once they are successfully onboarded for DARWIN EU and meet feasibility requirements for this study.

Exposure:

Covid-19 vaccines BNT162b2 (Comirnaty) and mRNA-1273 (Spikevax), particularly the number of received vaccine doses per brand.

For those databases where this information is available, the 4th dose (2nd booster) will be stratified for monovalent (original strain) or adapted, bivalent (original strain + omicron ba1 or original strain + omicron ba4/5).

Analyses will be conducted separately for each vaccine brand.

Primary outcomes of interest:

- 1) Outcomes assessed from start of rollout of 4th vaccine dose/ 2nd booster dose program onwards:
 1. COVID-19 related hospitalisation
 2. COVID-19 related death
- 2) Outcome/s during periods with dominance of any SARS-CoV-2 variants:
 3. All-cause mortality in the 3 months after discharge from a COVID-19 hospitalisation
 4. All-cause mortality in the 6 months after discharge from a COVID-19 hospitalisation
 5. Incidence of new-onset type 1 Diabetes Mellitus beyond the first 30d after SARS-CoV-2 infection
 6. Incidence of new-onset type 2 Diabetes Mellitus beyond the first 30d after SARS-CoV-2 infection
 7. Incidence of cardiovascular events (cerebrovascular disorders, dysrhythmias, ischemic and non-ischemic heart disease, pericarditis, myocarditis, heart failure and thromboembolic disease) in the 12 months after a SARS-CoV-2 infection

COVID-19 related hospitalisation (outcome 1, part of outcomes 3 and 4) is not available for IPCI and CPRD but will only be assessed in SIDIAP.

Study population:

All subjects aged 12 years and older, with at least 365 days of data availability before index date (ID) [ID defined as the date of the latest vaccine dose administered] AND data availability from 12/2020 onwards (i.e. the time when the roll-out of the vaccination campaign started) in the respective database will be included.

	Phase II C3-002 – Study Protocol							
	Author(s): [name], [name], [name]				Version: v2.1			
	Dissemination level: Public							

All studies will be carried out comparing the following cohorts, which we defined based on varying degrees of vaccine exposure and period of predominant SARS-CoV-2 variant as shown in Table 1 below.

COVID-19 vaccination history	Cohort number							
	1	2	3	4	5	6	7	8
1 dose only					x			
Complete primary vaccination course (monovalent only)	x	x	x	x		x	x	x
3rd dose, also called 1st booster (monovalent or any of the adapted, bivalent)	x	x	x	x			x	x
4th dose, also called 2nd booster (monovalent or any of the adapted, bivalent)		x						x
4th dose, also called 2nd booster (any of the monovalent)			x					
4th dose, also called 2nd booster (any of the adapted, bivalent boosters)				x				
Study period								
Start of roll-out 4 th dose/2 nd booster onwards	x	x	x	x				
XBB variant or later dominant	x	x	x	x				
Any variant dominant					x	x	x	x

*Cohorts 3 and 4 will only be created for databases where the vaccine product is reliably recorded in addition to vaccine brand.

Outcomes 1-2 will be assessed in cohorts 1-2 (and 3-4 where available), outcomes 3-7 will be assessed in cohorts 5-8.

Unvaccinated groups will not be used as a comparator in our study for vaccine effectiveness research because they may be very different from vaccinated individuals regarding their risk of infection with SARS-Cov-2. This study therefore focusses on the association of varying degrees of vaccine exposure and COVID-19 related outcomes.

Study period:

Period of “start of roll-out 4th dose/2nd booster dose onwards”: from 01/08/2022 - last available data for each database.

Period of “XBB variant or later dominant”: 01/03/2023 - last available data for each database. Note: This period is not covered by any of the data cuts onboarded for DARWIN EU at the time of protocol submission.

Period of “any variant dominant”: 01/01/2021 (when the wider roll-out of the vaccination campaign started) - last available data for each database.

Statistical analyses:

All analyses will be conducted separately for each database, and will be carried out in a federated manner, allowing analyses to be run locally without sharing patient-level data. For each analysis, we will subsequently pool effect estimates across databases using random effect meta-analyses, I² for heterogeneity will be reported.

Cell counts <5 will be suppressed to comply with the database’s privacy protection regulations.

	Phase II C3-002 – Study Protocol	
	Author(s): [name], [name], [name]	Version: v2.1
		Dissemination level: Public

Objective 1 and 2: Effectiveness of 2nd COVID-19 vaccine booster dose in people with 1 previous booster dose

Study population

People with a 3rd-vaccine dose (1st booster dose) of Comirnaty or Spikevax will be included from the source population. Cohorts will be generated separately for Comirnaty and Spikevax, respectively.

Study inclusion: Sequential matching

Inclusion will be conducted in a sequential manner as follows.

For each calendar week starting from the day when a 4th vaccine dose (i.e. 2nd booster vaccine) became available/recommended in the respective country, people will be assigned to two cohorts: people who received a 2nd booster dose that week (“boostered”) and people who did not receive a 2nd booster (“non-boostered”).

Using the first day of the respective week as “preliminary” index date for non-boostered people, and the date of the 4th vaccine dose for boostered people, the following inclusion criteria will be applied:

- At least 365 days of data availability in the respective database
- At least 90days of time elapsed since the last vaccine dose
- At least 90days of time elapsed since the last record of a clinical diagnosis of COVID-19 or positive SARS-COV-2 test.

Among those people in the boostered and non-boostered cohorts who met the inclusion criteria, non-boostered people will be match 1:1 to a boostered person, based on key confounders and large-scale propensity scores using nearest neighbor matching, with caliper width 0.2 standard deviation.

Key confounders will comprise but are not limited to:

- Age (e.g. 5-year age bands)
- Sex (exact)
- Geographic location (exact)
- Previous vaccine brands (e.g. homologous or heterologous vaccination scheme)
- Time from previous vaccination
- History of conditions for prioritization for vaccination
- Immunocompromised status
- Previous COVID-19 diagnoses (>90days before index date)

Large-scale propensity scores (PS) will be computed to estimate the probability of receiving a 4th vaccine dose. Covariates to be included in the large-scale PS will be selected from co-medications and comorbidities recorded prior to cohort-specific index dates. Among those, covariates with a prevalence below 0.5% in the study population will be omitted. Logistic regression with LASSO regularization will then be used for variable selection. The list of selected covariates will be manually screened by 2 epidemiologists/clinical domain experts to exclude potential instrumental variables.

With matching, non-boostered counterparts will be assigned the date of when the boostered counterpart received their 4th vaccine dose as their “final” index date (index date for the matched pair).

In the matched cohorts, people will be followed up from their index date until the earliest of

- End of their observation (i.e. date of data extraction, death)
- next vaccine dose (4th vaccine dose for non-boostered group, 5th vaccine dose for boostered group)
- COVID-19 related hospitalization or death

	Phase II C3-002 – Study Protocol	
	Author(s): [name], [name], [name]	Version: v2.1
		Dissemination level: Public

Follow-up will be censored for the matched pair if one counterpart is censored, but not if one counterpart experiences the outcome.

The same procedure will be conducted in the calendar week after, with previously non-boostered people being allowed to be included in the booster cohort once they change exposure status. Non-boostered people can only be matched once to a booster counterpart during the whole study.

All booster and matched non-boostered people from sequential weekly matching will be combined into the exposed and unexposed cohort for subsequent analyses.

Outcomes:

- COVID-19 related hospitalization will be assessed for SIDIAP and ICPI.
- COVID-19 related death will be assessed for CPRD, IPCI and SIDIAP.

Vaccine effectiveness analyses:

Cox proportions hazard models will be used to calculate hazard ratios (HR) for the outcomes of COVID-19 related hospitalisation and COVID-19 related death.

Negative control outcomes and empirical calibration for HR will be used as an additional measure to measure and minimise any potential residual confounding.

Kaplan-Meier plots and/or cumulative incidence plots will be used to illustrate survival analyses.

Vaccine effect waning:

Hazard ratios will be calculated for subsequent time windows after index date, i.e. in bi-weekly intervals.

Monthly intervals will be used in case of small event counts to increase sample size and power if needed.

Kaplan-Meier plots and/or cumulative incidence plots will be used to illustrate survival analyses.

Objectives 3-6: Post-acute COVID-19 complications

The following comparisons will be conducted for objectives 3-6:

- First-dose vaccinated vs. second-dose vaccinated [cohort 5 vs. 6]
- Second-dose vaccinated vs. 3rd dose vaccinated (1st booster dose) [cohort 6 vs 7]
- 3rd dose vaccinated vs. 4th dose vaccinated (2nd booster dose) [cohort 7 vs 8]

Objective 3 will be assessed for SIDIAP and IPCI only, whereas objectives 4-6 will be assessed in CPRD, IPCI and SIDIAP.

Study population

The study populations will be derived similar to the inclusion process outlined for objectives 1-2 above, including sequential matching.

For objectives 4 and 5, people with the respective outcome recorded anytime in their history will be excluded for the respective objective. For objective 6, an outcome-free washout window of 365 days prior to index date will be implemented.

Outcomes:

- COVID-19 hospitalization + death within 3/6 months from discharge
- SARS-CoV-2 infection + New onset diabetes Type 1 diabetes within 30-365 days after COVID-19
- SARS-CoV-2 infection + New onset diabetes Type 2 diabetes within 30-365 days after COVID-19
- SARS-CoV-2 infection + cardiovascular events (ccar) in the 12 months after a SARS-CoV-2 infection

	Phase II C3-002 – Study Protocol	
	Author(s): [name], [name], [name]	Version: v2.1
		Dissemination level: Public

For contextualization and interpretation of the study findings, we will also report the number of people with COVID-19 hospitalization and SARS-CoV-2 infections in each group, as these are part of the overall outcomes of “death following discharge from COVID-19 hospitalisation” and post COVID-19 complications.

Vaccine effectiveness analyses for COVID-19 related mortality following hospital discharge:

Incidence rates will be calculated for the matched cohorts and outcome. Cox proportional hazard models will be calculated for each outcome to provide HR. Negative control outcomes will be used as an additional measure to measure residual confounding. In the scenario of potential unmeasured confounding being detected by NCO, empirical calibration²⁵ for HR might be considered to minimise bias.

Kaplan-Meier plots and/or cumulative incidence plots will be used to illustrate survival analyses.

Vaccine effectiveness analyses for post-acute COVID-19 complications:

We will require at least 12 months of follow-up after SARS-CoV-2 infection to assess post-acute complications for outcomes 5, 6, and 7. If people die within 12months after COVID-19 they will contribute patient-time until death to the analyses. Only infections recorded 12months before the end of data availability will be included.

Incidence rates will be calculated for the matched cohorts and for each outcome. Cox proportional hazard models will be calculated for each outcome to provide HR. As previous research showed, no relevant difference in effect estimates was seen for post-COVID-19 symptoms when used fine-grey models accounting for death as competing risk compared to Cox regression.

Negative control outcomes will be used as an additional measure to measure residual confounding. A list of NCOs used in previous vaccine safety and effectiveness studies will be used. In the scenario of potential unmeasured confounding being detected by NCO, empirical calibration²⁵ for HR might be considered to minimise bias.

Kaplan-Meier plots and/or cumulative incidence plots will be used to illustrate survival analyses.

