Country	Name of Database	Justification for Inclusion	Health Care setting	Type of Data (EHR, claims, registries)	Number of active subjects	Feasibility count of outcome/exposure (if relevant)	Data lock for the last update	Contributing to objectives
United Kingdom	CPRD GOLD	Complete records on SARS-CoV-2 infection, Covid-19 vaccination, and outcome events of interest (excl. hospitalization for COVID-19)	Primary care	EHR	3M	Covid-19: 360,198 Comirnaty: 2,822,947 Spikevax: 311,069	01/2023	1-2 for outcome “COVID-19 related death” only, 4-6
The Netherlands	IPCI	Complete records on SARS-CoV-2 infection, Covid-19 vaccination, and outcome events of interest	Primary care	EHR	1.39M	Covid-19: 941,329 Comirnaty: 1,173,104 Spikevax: 463,315	12/2022	1-6
Spain	SIDIAP	Complete records on SARS-CoV-2 infection, Covid-19 vaccination, and outcome events of interest; Include inpatient admission information.	Primary care + linkage to hospital data	EHR	5.8M	Covid-19: 3,865,976 Comirnaty: 6,548,545 Spikevax: 3,371,395	06/2022	1-6

	Phase II C3-002 – Study Protocol	
	Author(s): [name], [name], [name]	Version: v2
		Dissemination level: Public

Clinical Practice Research Datalink GOLD, United Kingdom (University of Oxford)

The Clinical Practice Research Datalink (CPRD) is a governmental, not-for-profit research service, jointly funded by the National Institute for Health and Care Research and the Medicines and Healthcare products Regulatory Agency, a part of the Department of Health, United Kingdom (UK) (<https://cprd.com>). CPRD GOLD¹¹ comprises computerized records of all clinical and referral events in primary care in addition to comprehensive demographic information and medication prescription data in a sample of UK patients (predominantly from Scotland (52% of practices) and Wales (28% of practices). The prescription records include information on the type of product, date of prescription, strength, dosage, quantity, and route of administration. Data from contributing practices are collected and processed into research databases. Quality checks on patient and practice level are applied during the initial processing. Data are available for 20 million patients, including 3.2 million currently registered patients. Approval for this study was granted via the Research Data Governance Process.

Integrated Primary Care Information Project (IPCI), The Netherlands (Erasmus)

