8.3 Study Period

The study period will start on 01/01/2021 for all databases covering the period where “any variant” was dominant. The end of the study period will be the last available date of data collection for each contributing dataset.

For analyses conducted specifically at the time of predominance of “XBB variant or later dominant” variant, the study period would start on the 01/03/2023, when XBB became the dominant variant. However, this

	Phase II C3-002 – Study Protocol	
	Author(s): [name], [name], [name]	Version: v2.1
		Dissemination level: Public

period is not covered by the data cuts currently onboarded for DARWIN EU®. Analyses will therefore start at the time when vaccine booster programs offering the 4th vaccine dose were rolled out in each country.

Table 8.3.1. illustrates the periods of COVID-19 variant dominance across UK, The Netherlands and Spain.

Table 8.3.1. Periods of variant dominance

	UK	The Netherlands	Spain
Any variant	01/2021 - ongoing	01/2021 – ongoing	01/2021 - ongoing
Alpha and earlier variants	01/01/2021 - 01/06/2021	01/01/2021 – 01/07/2021	01/01/2021 – 01/07/2021
Delta	01/06/2021 – 15/12/2021	01/07/2021– 15/12/2021	01/07/2021– 15/12/2021
Omicron	15/12/2021 – 01/03/2023	15/12/2021 – 01/03/2023	15/12/2021 – 01/03/2023
XBB variant or later dominant	01/03/2023 - ongoing	01/03/2023 - ongoing	01/03/2023 - ongoing

<https://ourworldindata.org/grapher/covid-variants-bar?time=latest&facet=none&country=GBR~ESP~FIN~NOR~NLD>, accessed 15/08/2023

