8.8.3 Objectives 1-2: Vaccine effectiveness to prevent severe infection

Objectives 1 and 2 will assess the effectiveness of a 4th COVID-19 vaccine dose in people with 3 vaccine doses.

Study population

All people with a 3rd vaccine dose of Comirnaty or Spikevax will be included from the source population. Cohorts will be generated separately for Comirnaty and Spikevax, respectively.

Study inclusion: Sequential matching

Inclusion will be conducted using a sequential matching design, with similar designs being used in previous studies assessing vaccine effectiveness. Previous research showed matching to adequately reduce measured confounding in vaccine effectiveness research when including key variables such as geographic location²⁴.

Matching process using key confounders and Propensity Scores

For each calendar week starting from the day when a 4th vaccine dose (i.e. 2nd booster vaccine) became available/recommended in the respective country, people will be assigned to two cohorts: people who received a 4th vaccine dose during that week and people who did not receive a 4th dose.

Using the first day of the respective week as “preliminary” index date for non-boostered people, and the date of the 4th dose for booster-vaccinated people, the following inclusion criteria will be applied:

	Phase II C3-002 – Study Protocol	
	Author(s): [name], [name], [name]	Version: v2.1
		Dissemination level: Public

- At least 365 days of data availability in the respective database
- At least 90days of time elapsed since the previous vaccine dose (i.e. the 3rd or 4th vaccine dose)
- At least 90days of time elapsed since the last record of a clinical diagnosis of COVID-19 or positive SARS-COV-2 test.

Among those people in the cohorts who received or not received a 4th dose and met the inclusion criteria, non-boostered people will be matched 1:1 to a person receiving their 4th dose, based on key confounders and large-scale propensity scores using nearest neighbor matching, with caliper width 0.2 standard deviation. Key confounders will comprise but are not limited to:

- Age (e.g. 5-year age bands)
- Sex (exact)
- Geographic location (exact)
- Previous vaccine brands (e.g. homologous or heterologous vaccination scheme)
- Time from previous vaccination
- History of conditions for prioritization for vaccination
- immunocompromised status
- previous SARS-CoV-2 diagnosis (>90days before index date)

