Large-scale propensity scores (PS) will be computed to estimate the probability of receiving a 4th vaccine dose. Covariates to be included in the large-scale PS will be selected from co-medications and comorbidities recorded prior to cohort-specific index dates. Among those, covariates with a prevalence below 0.5% in the study population will be omitted. Logistic regression with LASSO regularization will then be used for variable selection. The list of selected covariates will be manually screened by 2 epidemiologists/clinical domain experts to exclude potential instrumental variables.

The same procedure will be conducted in the calendar week after, with previously non-boostered people being allowed to be included in the booster cohort once they change exposure status. Non-boostered people can only be matched once to a booster counterpart during the whole study. With matching, non-boostered counterparts will be assigned the date of when the booster counterpart received their 4th vaccine dose as their “final” index date (index date for the matched pair).

All booster and matched non-boostered people from sequential weekly matching will be combined into the booster and non-boostered cohort for subsequent analyses. The study inclusion and sequential matching process is illustrated in [Figure 8.8.3.1](#) below.

[figure not shown]

	Phase II C3-002 – Study Protocol	
	Author(s): [name], [name], [name]	Version: v2.1
	Dissemination level: Public	

Figure 8.8.3.1 Study inclusion and sequential matching process

	Phase II C3-002 – Study Protocol	
	Author(s): [name], [name], [name]	Version: v2.1
		Dissemination level: Public

Follow-up

In the matched cohorts, people will be followed up from their index date until the earliest of

- End of their observation (i.e. date of data extraction, death)
- 2nd booster vaccination for unvaccinated group, 3rd booster for vaccinated group etc.
- COVID-19 related hospitalization or death, with outcome date being defined as the date of first COVID-19 diagnosis/positive test related to hospitalization or death.

Follow-up will be censored for the matched pair if one counterpart is censored, but not if one counterpart experiences the outcome.

Outcomes

The outcomes are defined in detail in section 8.6.2.

COVID-19 related hospitalization will be assessed for SIDIAP and IPCI. COVID-19 related death will be assessed for CPRD, IPCI and SIDIAP.

Statistical Analyses

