
11. LIMITATIONS OF THE RESEARCH METHODS

General limitations:

- The study will be informed by routinely collected health care data and so data quality issues must be considered.
- We will use large-scale propensity scores to minimize measured confounding, and NCOs to assess potential residual confounding. However, given the observational nature of our data, we cannot rule out remaining confounding, which could partially account for findings in this study.

Study-specific limitations:

- Mandatory PCR test for people who tested positive in lateral flow home tests were skipped in early 2022. As not all positive home tests were reported and recorded as clinical diagnoses in primary care databases, it is likely that non-severe SARS-CoV-2 infections are underreported after 02/2022. Moreover, underreporting of COVID-19 for asymptomatic case is to be expected. Underreporting of COVID-19 could lead to misclassification of outcomes for Objectives 4-6, namely post-acute COVID-19 complications (diabetes, cardiac events). For objectives 4-6, we require a minimum follow-up time of 12months after SARS-CoV-2 to identify cases of new-onset diabetes and/or cardiovascular complications. With this, only infections recorded before 02/2022 will be included in the study.
- Routine screening has been impacted by the pandemic, and therefore diagnoses of new conditions, e.g. T2DM might have been delayed depending on testing practices.
- COVID-19 related hospitalization is unlikely to be underreported as people are likely to be asked about previous SARS-CoV-2 infections at hospital admission (Objective 3). However, positive COVID-19 test results that occur around hospitalization do not constitute a hospitalization *due to* COVID-19.

	Phase II C3-002 – Study Protocol	
	Author(s): [name], [name], [name]	Version: v2.1
		Dissemination level: Public

We will use the data cuts currently onboarded for DARWIN EU for CPRD, IPCI and SIDIAP. However, none of those is currently covering the period of XBB variant predominance. We therefore designed the study to assess objectives 1 and 2 to start at the time the 4th vaccine doses were made available for people.

MANAGEMENT AND REPORTING OF ADVERSE EVENTS/ADVERSE REACTIONS

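### The abstract's 01/08/2022 start for Objectives 1-2 falls after SIDIAP's 06/2022 data lock, and the competing start rule, national 4th-dose roll-out, carries no date

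*Protocol*

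**What the plan says.** The abstract, under Study period, defines the period that governs cohorts 1-4 (outcomes 1 and 2, Objectives 1-2) as "from 01/08/2022 - last available data for each database". It makes no distinction by country.

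Table 8.2.1 in section 8.2 gives these data locks: SIDIAP 06/2022, IPCI 12/2022, CPRD GOLD 01/2023. SIDIAP and IPCI are each listed for objectives 1-6. CPRD is listed for objectives 1-2 for COVID-19 death only, and for objectives 4-6. Section 11 states: "We will use the data cuts currently onboarded for DARWIN EU for CPRD, IPCI and SIDIAP".

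Other places use a different start. Section 8.3 says: "Analyses will therefore start at the time when vaccine booster programs offering the 4th vaccine dose were rolled out in each country". The matching text in section 8.8.3 begins with the week in which a 4th dose "became available/recommended in the respective country, people will be assigned to two cohorts", and the abstract's own matching paragraph follows the same rule. Table 7.1A and section 11 also tie the start to roll-out or availability. None of these gives a date for any country.

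On outcomes, section 8.8.3 says "COVID-19 related hospitalization will be assessed for SIDIAP and IPCI" and "COVID-19 related death will be assessed for CPRD, IPCI and SIDIAP". The abstract, after its list of outcomes, says that COVID-19 hospitalisation "is not available for IPCI and CPRD but will only be assessed in SIDIAP".

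**The concern.** Three statements cannot all hold: a start on 01/08/2022, a SIDIAP cut locked in 06/2022, and SIDIAP contributing to Objectives 1-2. The protocol discloses that no cut reaches the XBB period, and sections 8.3 and 11 offer a start at 4th-dose roll-out as the way round this. Nowhere does it say that, on the one date it gives for that roll-out period, SIDIAP is not covered either.

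At stake is which databases can answer Objectives 1-2. Someone who programs the abstract's date gets an empty SIDIAP cohort. Someone who programs the roll-out rule must first choose a Spanish date that the protocol does not supply. The choice decides whether hospitalisation has a second database, whether there is anything to pool for that outcome, and how many databases support COVID-19 death. For waning (Objective 2), the calendar window also caps how far after the index date any hazard ratio can be estimated.

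**Working it through.** The protocol states no sample size, event count or person-time for Objectives 1-2, so there is no figure to reproduce. The check is date arithmetic.

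**Inputs**
- Start S = 01/08/2022 (abstract, Study period).
- Data locks L (Table 8.2.1): SIDIAP 06/2022, IPCI 12/2022, CPRD GOLD 01/2023. Only months are given, so each lock is taken at the first and at the last day of its month.
- No refresh of the cuts (section 11).

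**Formula**

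Calendar days available = max(0, L − S + 1), counting both end days.

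| Database | Lock, first day of month | Lock, last day of month | Days available |
|---|---|---|---|
| SIDIAP | 01/06/2022: 61 days before S | 30/06/2022: 32 days before S | 0 |
| IPCI | 01/12/2022: 123 | 31/12/2022: 153 | 123 to 153 |
| CPRD GOLD | 01/01/2023: 154 | 31/01/2023: 184 | 154 to 184 |

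For SIDIAP, 30/06 to 01/08 is 1 + 31 = 32 days, and 01/06 to 01/08 is 30 + 31 = 61 days. Wherever in June the lock falls, the result is zero.

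The figures for IPCI and CPRD are ceilings. Only a pair matched on the first day could be followed for the whole window, and pairs matched later have less.

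**What follows under the abstract's date**
- *Hospitalisation, with sources as in the abstract's Objectives 1-2 text and sections 8.2 and 8.8.3 (SIDIAP and IPCI):* IPCI alone, at most 153 days. With one database there is nothing to pool.
- *Hospitalisation, with the source as in the abstract's outcome list (SIDIAP only):* no database.
- *COVID-19 death:* CPRD and IPCI. Pooling remains possible across two databases instead of three.

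**What follows under the roll-out rule**

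SIDIAP's window would be its lock minus the Spanish roll-out date. The protocol gives no such date, so the window could be positive or zero. It cannot be computed from this document.

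**Objectives 3-6**

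Their period starts on 01/01/2021 (abstract and section 8.3), well before every lock. This clash does not reach them.

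**The case against.** The strongest reply is that the methods text, not the abstract, is operative. Section 8.3, section 8.8.3, Table 7.1A and section 11 all start at national roll-out, and section 11 says Objectives 1-2 were designed this way because of the limits of the cuts. If Spain's roll-out came before the lock, SIDIAP contributes and only the abstract's date is wrong. This stands as a limit on the conclusion: zero SIDIAP person-time is conditional on the abstract's date. It does not remove the contradiction, because 01/08/2022 is the only date given and no Spanish date is stated against which to check the lock.

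A second reply is that the last available data could mean a later cut. Section 11 commits to the current ones. If a later one is meant, Table 8.2.1 should show it.

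A reader might also infer more than the document supports:

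- *That hospitalisation has no data at all.* This needs the abstract's date and also the abstract's SIDIAP-only sentence. That sentence conflicts with the abstract's own Objectives 1-2 text and with sections 8.2 and 8.8.3. Section 8.8.4 likewise uses IPCI, for mortality after hospital discharge. It is a separate inconsistency.
- *That three-database evidence on hospitalisation is lost.* None was planned; CPRD is excluded from that outcome throughout. Nor is SIDIAP clearly the only linked source: Table 8.2.1 names hospital linkage for SIDIAP alone, but the text of section 8.2 attributes hospitalisation information to IPCI as well.
- *That 57% of the evidence goes.* SIDIAP holds 5.8M of 3 + 1.39 + 5.8 = 10.19M active subjects (0.569), but Objectives 1-2 need three earlier doses and 90-day gaps. The protocol gives no counts of 3rd- or 4th-dose recipients, so this share does not measure the loss.
- *That the whole primary question fails.* Table 7.1 labels Objectives 1-2, 3 and 4-6 all as primary.

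**Conclusion.** The point holds as an unreconciled contradiction in dates. On the only calendar date the protocol gives for Objectives 1-2, SIDIAP's cut ends 32 to 61 days too early and supplies no index dates or person-time, although it is listed for those objectives. Hospitalisation then rests on IPCI alone, or on nothing if the conflicting abstract sentence is followed, and COVID-19 death rests on CPRD and IPCI, with ceilings of about 6 and 5 months. Under the roll-out rule SIDIAP's contribution is unknown; a flat statement that SIDIAP contributes nothing would go beyond the document.

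The conclusion assumes that the lock falls within June 2022, that the abstract's date applies to every database as written, and that the cuts are not refreshed. Because the clash decides which databases can answer Objectives 1-2, it should be corrected in the protocol before the analysis is run.

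**What to change.** 1. Replace the two start rules with one dated start per country for Objectives 1-2. Use it in the abstract, Table 7.1A and sections 8.3, 8.8.3 and 11, and check each date against that database's lock in Table 8.2.1.
2. If the Spanish start falls before SIDIAP's lock, correct the abstract's date and state how much SIDIAP follow-up is available.
3. If it does not, choose one of two routes:
   - name a later SIDIAP cut and its date in Table 8.2.1 and section 11; or
   - remove SIDIAP from Objectives 1-2 in Table 8.2.1, Table 7.1A, the abstract and section 8.8.3, state that hospitalisation is IPCI-only (or not assessed) and cannot be pooled, and limit pooling of COVID-19 death to CPRD and IPCI.
4. Reconcile the abstract's SIDIAP-only sentence on hospitalisation with the abstract's Objectives 1-2 text and sections 8.2, 8.8.3 and 8.8.4, which include IPCI.

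The cost is protocol wording, plus one data refresh if a later cut is chosen. If SIDIAP is removed, the study claims less hospitalisation evidence for Objectives 1-2.
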